### **Research objectives:**

1. To conduct a comparative assessment of the dynamics of nutritional deficiency and nutritional status of patients operated on for malignant tumors of the hepatopancreatoduodenal zone in the early postoperative period during isolated enteral, isolated parenteral and mixed types of nutritional support.
2. To analyze the dynamics of the state of protein and carbohydrate metabolism, the consistency of liver function in cancer patients operated on for malignant tumors of the hepatopancreatoduodenal zone, against the background of isolated enteral, isolated parenteral and mixed type of nutritional support in the early postoperative period.
3. To determine the degree of effectiveness of these methods of nutritional support in this category of patients based on the totality of the results of assessing nutritional status and the dynamics of the level of basal metabolism in patients in the early postoperative period.

**Introduction.** Treatment of malignant tumors of the hepatopancreatobiliary zone is one of the most pressing problems in clinical oncology. Among diseases of the liver and extrahepatic biliary tract, the most severe can be considered those that are accompanied by persistent obstruction of the main bile ducts with the subsequent development of obstructive jaundice (MJ), the treatment of which is still controversial.

Despite the increased availability of various highly sensitive non-invasive methods for diagnosing tumors of these organs, the detection of cancer of these organs in the early stages of the disease has practically not increased. In the vast majority of cases, patients continue to be admitted to specialized hospitals only with the development of various complications of cancer of the pancreatoduodenal zone, such as obstructive jaundice, duodenal obstruction, hepatic-renal failure, tumor invasion of hollow organs and bleeding into the lumen of the gastrointestinal tract (Patyutko Yu.I., Kotelnikov A.G., 2007).

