### Research objectives:

1. To conduct a comparative assessment of the dynamics of nutritional deficiency and nutritional status of patients operated on for malignant tumors of the hepatopancreatoduodenal zone in the early postoperative period during isolated enteral, isolated parenteral and mixed types of nutritional support.
2. To analyze the dynamics of the state of protein and carbohydrate metabolism, the consistency of liver function in cancer patients operated on for malignant tumors of the hepatopancreatoduodenal zone, against the background of isolated enteral, isolated parenteral and mixed type of nutritional support in the early postoperative period.
3. To determine the degree of effectiveness of these methods of nutritional support in this category of patients based on the totality of the results of assessing nutritional status and the dynamics of the level of basal metabolism in these patients in the early postoperative period.

Researched 91 patients, will be divided into 3 groups:

1. The first group (n=31) included patients who received enteral nutrition (EN) after surgery.
2. The second group (n=30) included patients receiving parenteral nutrition (PN).
3. The third group (n=30) receiving mixed nutrition (MN), as is commonly considered the method of partial parenteral nutrition, in the early postoperative period.

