A comparative analysis of the dynamics of ALT and ASAT values in all patients in the study groups on the 2-3, 6-8, 10-12 days of the postoperative period reflected an excess of their normal values after surgery in some patients tens of times in the first day of the postoperative period. These changes can be explained, first of all, by the surgical intervention itself and its volume, the underlying disease of the hepatopancreatoduodenal zone and the associated cytolytic syndrome against the background of cholestasis [9,10,11].

In terms of assessing the dynamics of blood transaminase levels, in the majority of patients in the first group (78.2%), by the 5th and 10th days there was a decrease in ALT and AST values, on average, by 32.1 and 40.15%, respectively.

In the overwhelming number of patients in the second group (81.6%,  $n=26$ ), a statistically significant decrease in the level of these blood transaminases was also recorded, on average by 72.2% by the fifth day and 66.7% by the 10th day of the postoperative period from level of their initial indicator.

With a mixed type of nutritional support, by the 5th day of the postoperative period, the average significant decrease in transaminases was, on average, up to 72.6% of the initial values ( $p = 0.000$ ); by the 10th day of the postoperative period, their level decreased to 63.8% from the previous achieved value of 5 days ( $p=0.008$ ).

When comparing analyzes of the level of total blood bilirubin in patients of all nutrition groups, there was a strong direct correlation with a decrease in the level of blood transaminases, which, apparently, was also due to the creation of sufficient intraoperative bile outflow due to drainage of the biliary tract and elimination of the cause of obstructive jaundice (tumor).

However, high values of total blood bilirubin that persisted on the first day after surgery were due to temporary swelling of the biliary tract, which caused the excess of the norm by more than 10 times ( $p = 0.000$ ).

On days 5-7, there was a tendency towards a 5-6 fold decrease in its level from the initial values, which gradually decreased to normal values by days 10-12 and in some patients persisted until discharge from the hospital ( $p = 0.004$ ).

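### The printed transaminase falls cannot support the between-arm liver-function comparison that objective 2 asks for

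*Combined protocol and SAP*

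**What the plan says.** Item 2 of the Research objectives, given in the protocol and repeated in the Report, covers "the consistency of liver function in cancer patients operated on for malignant tumors" under each of the three types of support. The Report's group list begins "The first group (n=31) included patients who received enteral nutrition (EN) after surgery" and gives n=30 for each of the other two arms.

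The transaminase results are in Results and discussion, which follows Methods of statistical data analysis in the Report:

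- **Enteral:** "in the majority of patients in the first group (78.2%), by the 5th and 10th days there was a decrease". The mean falls attached to this share are 32.1% and 40.15%, linked to the two enzymes and the two days only by the word *respectively*. No count and no reference value are given.
- **Parenteral:** "In the overwhelming number of patients in the second group (81.6" per cent, with n=26 beside it). The mean falls are 72.2% by day 5 and 66.7% by day 10, both from the initial value.
- **Mixed:** no subset is named. The day-5 figure, 72.6%, is tied to the initial values. For day 10, "by the 10th day of the postoperative period, their level decreased to 63.8% from the previous achieved value of 5 days".

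The text introducing these results speaks of all patients and lists postoperative days 2-3, 6-8 and 10-12. The statistical methods text describes a three-group test followed by pairwise tests. No between-arm test is printed for transaminases, and the Conclusion does not mention them.

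**The concern.** A between-arm comparison needs the same patients (everyone with a value), the same reference value and the same kind of figure in each arm. Here all three appear to differ.

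If a mean fall is taken only over patients whose values fell, the patients have been selected on the outcome. The mean then exceeds the all-patient mean whenever the rest did not improve. If this was done in two arms and not in the third, the contrast with the third arm is distorted too. A day-10 figure relative to day 5 cannot be set beside one relative to the initial value without conversion, and the conversion depends on how the mixed day-5 figure is read.

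At stake is the transaminase part of the answer to objective 2. No numbered conclusion rests on these figures, so the damage stays within that objective.

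**Working it through.** **1. Do the printed shares fit the arms?** Inputs: arm sizes 31 and 30 (Report, Research objectives); shares 78.2% and 81.6% with n=26 (Results and discussion).

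- Parenteral: 26/30 = 86.7%, not 81.6%. Working backwards, 26/0.816 = 31.9 patients, in an arm of 30. Neither 26/31 = 83.9% nor 26/32 = 81.25% rounds to 81.6%.
- Enteral: 0.782 × 31 = 24.2 patients. The nearest counts give 24/31 = 77.4% and 25/31 = 80.6%, so no count out of 31 gives 78.2%.

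Neither share is reproduced.

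**2. How much could improvers-only averaging matter?** Let p be the share who improved, d their mean percentage fall, and c the mean percentage rise in the others. Then

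all-patient mean fall = p × d − (1 − p) × c.

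The documents do not give c. I take c = 0 as the reference assumption and show c from −10% (the others fell by 10%) to +20%. I take 32.1% as the enteral day-5 figure.

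| Day 5 | Printed | c = −10% | c = 0 | c = +20% |
|---|---|---|---|---|
| Enteral, p = 78.2% | 32.1% | 27.3% | 0.782 × 32.1 = 25.1% | 20.7% |
| Parenteral, p = 81.6% | 72.2% | 60.8% | 0.816 × 72.2 = 58.9% | 55.2% |
| Parenteral, p = 26/30 | 72.2% | 63.9% | 0.867 × 72.2 = 62.6% | 59.9% |

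Both values of p are shown for the parenteral arm because the text contradicts itself there.

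**3. Mixed arm, day 5.** The sentence speaks of a decrease but expresses it as a share of the initial values.

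- Read as the level reached: fall = 100 − 72.6 = 27.4%. Order of the printed falls: parenteral 72.2, enteral 32.1, mixed 27.4.
- Read as the size of the fall: 72.6%. Order: mixed 72.6, parenteral 72.2, enteral 32.1.

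The mixed arm moves from last to first on wording alone.

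**4. Mixed arm, day 10, on the initial-value scale.** Taking the day-10 sentence as printed, the level is 63.8% of the day-5 level.

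- Day-5 level 72.6%: 0.726 × 0.638 = 0.463, so 46% of initial.
- Day-5 level 27.4%: 0.274 × 0.638 = 0.175, so 17% of initial.

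The printed parenteral day-10 level is 100 − 66.7 = 33.3% of initial. The enteral figure cannot be placed with certainty, because its reference value is not stated.

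**The case against.** **The averaging is inferred.** The text opens by referring to all patients, and it never states the denominator of the means. The 78.2% and 81.6% could be shares printed beside means taken over the whole arm. This stands as a limit: improvers-only averaging is the natural reading, not an explicit statement, and the true bias cannot be computed because nothing is reported for the other patients.

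**The reference-day mismatch is narrow.** The mixed day-5 figure does use initial values, so the mismatch affects day 10 only. Once the day-5 reading is settled, a multiplication removes it. This also stands.

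**The day-10 order.** A reader might infer that the mixed and parenteral arms also change places at day 10 according to the reading, since 46% and 17% lie on either side of 33%. The documents do not support that as a finding. It sets a mixed figure with no named subset against a parenteral figure that probably covers improvers only. With zero change in the other patients, the parenteral fall is 0.816 × 66.7 = 54.4%, close to the 53.7% for mixed on the level reading. Above a rise of about 4% in those patients, the mixed arm is lower on both readings. With p = 26/30 that threshold is about 31%. Further readings that treat 63.8% as the size of the day-10 fall go against the printed wording.

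**No ranking is claimed.** The report prints no transaminase ranking, so the orders above are only those its figures imply. The day-5 order also assumes that *respectively* in the enteral sentence means day 5 and day 10. It could mean ALT and AST.

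**A figure is not shown** in the text available here and may give the levels. It would not reconcile shares and counts that disagree in print.

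**Conclusion.** The concern holds: as printed, the transaminase results cannot support the between-arm comparison in objective 2. Three points rest on the text alone: the shares do not match the arms, the day-10 reference differs between the mixed and parenteral arms (and is unstated for enteral), and the mixed day-5 figure has two readings 45.2 percentage points apart (72.6 − 27.4).

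The fourth point, overstatement from averaging over improvers, depends on the natural reading and on the other patients not having improved. With zero change assumed, the enteral fall drops from 32.1% to about 25% and the parenteral fall from 72.2% to about 59% or 63%, depending on p. These figures illustrate the effect; they do not estimate it. Under the same assumption the enteral fall of 25.1% lies below the mixed 27.4%, so the move from last to first describes the printed falls only.

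A reader might infer that the report wrongly claims an advantage for mixed support on transaminases, or that the arms' true order is known to reverse. The documents support neither. Confidence is medium. The point should be corrected, although no numbered conclusion depends on it.

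**What to change.** Report ALT and AST separately, for all patients in each arm who have a value. Express each as a ratio to one stated baseline at the days actually sampled, with a 95% CI and the number analysed. The preoperative value is the natural baseline, since the bilirubin results already use it. The baseline must be named: *initial* is not defined for transaminases, the basal-metabolism text ties it to postoperative days 1-2, and the report describes a steep rise on the first postoperative day.

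Compare the arms directly, preferably on the log scale with adjustment for the baseline value. Give the share who improved as a separate proportion with its count and true denominator, and reconcile 81.6% with n=26 and 78.2% with the arm of 31.

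The cost is a re-analysis of values already collected. The printed falls may change, and not necessarily in one direction if the baseline changes as well. The days listed (2-3, 6-8, 10-12) do not guarantee a day-5 value for every patient, so patients without a value at a given day must be counted and shown.

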As can be seen from the presented data, in the preoperative period, according to the SGA assessment, 24 patients in the enteral group, 19 patients in the parenteral group, and 17 patients in the mixed group had normal nutritional status before surgery, with variations relative to patients with moderate to severe malnutrition. Assessment of nutritional status before surgery using the NRI scale allowed us to confirm the nutritional status of the vast majority of patients in all groups as relatively normal

Thus, in 62 of the 91 patients examined, the NRI was assessed as true negative (normal nutritional status), in 26 as true positive (moderate malnutrition), and in 3 as severe malnutrition. Data from the NRI method during this time period had a strong correlation with the results of the SGA scale ( $p < 0.005$ ).

On the 10-12th day of the postoperative period in patients of the “enteral” group, the results of the assessment on the SGA scale remained unchanged; according to the NRI rating scale, there was an increase in “moderate malnutrition” per patient (25%).

With parenteral nutritional support, 17 patients had “normal nutrition”, 14 patients had moderate malnutrition, with regression of “severe malnutrition” in 1 patient. In the mixed nutrition group, there was a complete elimination of signs of “severe malnutrition” by 100% according to the given scales ( $p < 0.005$ ).

In patients of all study groups, throughout the entire period of nutritional support, fluctuations in the level of basal metabolism were observed in average values of  $335.89 \pm 53.6$  kcal/day (13.44%) from the initial value - 1-2 days of the postoperative period and were due to variability body mass index and the dynamics of the temperature curve after surgery.

In patients in the groups with enteral and parenteral nutrition, by the end of these types of energy subsidies (days 10-15), the level of basal metabolism was observed to approach its initial values -  $2500.1 \pm 353.4$  kcal/day and  $2350.0 \pm 330.5$  kcal/day days accordingly. With a mixed type of nutrition, there was a statistically significant decrease in the level of basal metabolism by 6.78% ( $2250.0 \pm 105.2$  kcal/s), which allows us to conclude that patients' energy costs are more effectively covered with this option of nutritional support in a comparative aspect with isolated types nutrition ( $p < 0.03$ ).

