In comparative quantitative terms, in patients of the first group, a decrease in the level of total bilirubin was recorded, on average, by 12.7% only by the 10th day after surgery ( $p = 0.187$ ). In the second group, there was a decrease in the level of total blood bilirubin by the 5th day, on average, by 40.09% and by the 10th day by 45.0% from its initial values (preoperative period), ( $p = 0.002$ ).

In patients of group 3, there was a slower regression of this indicator: a decrease, on average, by 20.0% by the 5th day and by 44.0% by the 10th day of the postoperative period [1,5,12].

[figure not shown]

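### The report measures percentage change from different or undated reference points, so the ALT, AST and bilirubin falls in the three feeding groups are not on one scale

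*Combined protocol and SAP*

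**What the plan says.** All the results in question are in the report, in the Results and discussion text under Methods of statistical data analysis.

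- **Basal metabolism, all groups.** The fluctuation is "kcal/day (13.44%) from the initial value - 1-2 days of the postoperative period".
- **Total bilirubin, group 2 (parenteral).** The level fell by day 5 "by 40.09% and by the 10th day by 45.0% from its initial values (preoperative period". For group 3 (mixed) the falls are 20.0% by day 5 and 44.0% by day 10, with no date for the reference. For group 1 (enteral) the fall is 12.7%, only by day 10.
- **ALT and AST, group 1.** "by the 5th and 10th days there was a decrease in ALT and AST values, on average, by 32.1 and 40.15%, respectively". No reference is named. The wording also leaves open whether the two figures belong to the two days or to the two enzymes.
- **ALT and AST, group 2.** The levels fell "on average by 72.2% by the fifth day and 66.7% by the 10th day of the postoperative period from level of their initial indicator". The indicator is not dated.
- **ALT and AST, group 3.** By day 5, "the average significant decrease in transaminases was, on average, up to 72.6% of the initial values". The day-10 figure, 63.8%, is expressed against the value reached on day 5.

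The transaminase paragraph names only postoperative sampling windows (days 2-3, 6-8 and 10-12). It says values exceeded normal "in some patients tens of times in the first day of the postoperative period". The statistical methods list a baseline, day 5 and day 10 for within-group tests but do not date the baseline. The protocol's Data analysis and monitoring section does not mention a reference for change.

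**The concern.** Objective 2, in both the protocol and the report, is to compare protein and carbohydrate metabolism and liver function under the three feeding routes. The transaminase and bilirubin results are given as percentage falls, and the text gives no ALT, AST or bilirubin levels. A percentage fall can be compared between groups only if every group is measured from the same point.

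The choice matters most for a marker that rises sharply with the operation. A fall from the first postoperative value mainly describes recovery from the surgical surge. A fall from the preoperative value describes whether the patient is better than before surgery. These are different quantities, and the report does not say which one it prints for ALT and AST.

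**Working it through.** **What can be reproduced.** The 72.2% and 66.7% falls cannot be, because no ALT or AST level is printed. The basal-metabolism percentage is coherent: 335.89 / 0.1344 = 2,499 kcal/day, close to the 2,500.1 kcal/day given for the enteral group at the end of support. That supports the arithmetic but does not date the reference.

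**Step 1. Day-10 transaminases, groups 2 and 3.** Group 2 is 66.7% below its initial indicator. Group 3's 63.8% is relative to day 5. Both group 3 figures can be read as *to* or *by*. With a the day-5 level as a fraction of initial and b the day-10 level as a fraction of day 5, the day-10 fall from initial is 1 − a × b.

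| Day-5 reading | Day-10 reading | Level, a × b | Fall from initial |
|---|---|---|---|
| to 72.6% (a = 0.726) | to 63.8% (b = 0.638) | 0.463 | 53.7% |
| to 72.6% (a = 0.726) | by 63.8% (b = 0.362) | 0.263 | 73.7% |
| by 72.6% (a = 0.274) | to 63.8% (b = 0.638) | 0.175 | 82.5% |
| by 72.6% (a = 0.274) | by 63.8% (b = 0.362) | 0.099 | 90.1% |

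Against 66.7% in group 2, group 3 does worse on the first reading and better on the other three. The chaining treats average percentages as if they described one group level, which is an approximation.

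**Step 2. The same comparison from day 5.** Group 2's level is 1 − 0.722 = 0.278 of initial at day 5 and 1 − 0.667 = 0.333 at day 10. The ratio is 0.333 / 0.278 = 1.20, a rise of about 20% from day 5. Group 3's change over the same interval is a fall of 36.2% or 63.8%. The printed 66.7% and 63.8% look alike only because they have different denominators.

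**Step 3. Bilirubin.** The general text reports a 5-6 fold fall from undated initial values by days 5-7: 1 − 1/5 = 80.0% and 1 − 1/6 = 83.3%. By day 5 the printed group falls are 40.09% (group 2) and 20.0% (group 3), and no group exceeds 45.0% even by day 10. A shift from the early postoperative peak to the preoperative value would explain the gap. Assume that shift, take group 3's reference as preoperative too, and treat day 5 and days 5-7 as one time. The implied ratio of peak to preoperative level is then 0.5991 × 5 to 0.5991 × 6 = 3.0 to 3.6 in group 2, and 0.80 × 5 to 0.80 × 6 = 4.0 to 4.8 in group 3. This is a possible explanation, not something the report states.

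**Step 4. What a peak reference would mean for ALT and AST.** Let k be the ratio of peak to preoperative level; the documents do not give it. If group 2's 72.2% were measured from the peak, the day-5 level would be 0.278k of the preoperative level: 0.556 at k = 2, 1.00 at k = 1/0.278 = 3.60 and 1.39 at k = 5. For the 66.7% at day 10, break-even is 1/0.333 = 3.00. If the reference is preoperative, the day-5 level is 27.8% of the preoperative level whatever the surge.

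**The case against.** The best defence is that the documents lean towards a preoperative reference for liver tests. The protocol's study plan (section III) lists transaminases and provides for tests before and early after surgery, although that item's parenthesis mentions only body composition. The statistical methods use a baseline, day 5, day 10 structure, and group 2 bilirubin is explicitly preoperative. The days 1-2 gloss concerns basal metabolism, a calculated quantity. Weights were scheduled before surgery and on days 5, 10 and 15, so a value for days 1-2 may simply use the preoperative weight. This makes a preoperative reading of ALT and AST plausible. It does not date that reference, name one for group 1, or remove the day-5 denominator in group 3.

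A reader might infer two stronger things. One is that the printed transaminase falls are really worsenings. That needs both a peak reference and a surge above 3.60-fold at day 5, and neither is documented. The *tens of times* remark is relative to normal, applies to some patients, and is attributed also to the underlying disease and cholestasis, so preoperative values may already have been high. The other is that the falls rank the groups by size of operation. The documents give no operation mix or peak value by group, so this too is unsupported.

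It is also fair that feeding starts after surgery, so an early postoperative reference is arguable if it is labelled. No item in the report's Conclusion rests on ALT, AST or bilirubin.

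**Conclusion.** The point holds as a problem of inconsistent and undated reference points. Without any assumption about a surge, group 3's day-10 transaminase figure and group 2's have different denominators and cannot be compared. On a common denominator group 3's fall lies anywhere from 53.7% to 90.1%, against 66.7%, subject to the chaining approximation. The bilirubin text (80% to 83% against 40.09% and 20.0%) suggests a shifting reference but does not prove one, since the time windows differ slightly.

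If the transaminase reference is the postoperative peak, a fall need not mean improvement on the preoperative level; whether that happened cannot be told from the documents. The effect is on the liver-function part of Objective 2. The basal-metabolism conclusion also refers to initial values and needs the same definition. A figure that is not reproduced in the available text might date the reference, so the finding applies to the text as it stands.

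**What to change.** In the report's Methods of statistical data analysis, state one reference for all percentage changes: the last preoperative test, in line with the protocol's before-and-after testing and with the bilirubin gloss for group 2. Then:

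- Recompute the day-5 and day-10 changes in ALT, AST and bilirubin from that reference in all three groups. Print the levels beside the percentages, and write *by* or *to* without ambiguity.
- Make the reference for basal metabolism consistent with it.
- Report the first postoperative value separately, and label any change measured from it as peak-referenced. If preoperative ALT or AST values were not kept, say so and use that label throughout.

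The cost is a recalculation from stored values. The downside is that the printed percentages, and with them the apparent order of the groups, may change.

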## **Methods of statistical data analysis**

All patients hospitalized for special treatment with a verified diagnosis of a malignant neoplasm were subjected to the study in the abdominal department of the KGP at the Regional Oncological Dispensary, Karaganda.

The quantitative and qualitative indicators obtained during the study were analyzed using descriptive and analytical statistics methods. For statistical processing of qualitative (diagnosis codes, dichotomous data) and quantitative variables: symptom intensity, severity, frequency of occurrence, we used the calculation of the median level (Me) with 25%-75% quartiles (Q25; Q75) and the calculation of the arithmetic mean (M) with error (m) and 95% confidence interval (95% CI), standard deviation (s). Quantitative variables were checked for normality of distribution using the Kolmogorov-Smirnov test, as well as the module of Skewness and Kurtosis for quantitative variables  $| \leq 2 |$ . Differences in the 3 groups of patients for quantitative variables corresponding to a normal distribution were identified using the Student's t test for unrelated groups, first for 3 or more groups, and then in pairs for each pair using the Student's t test. Differences for rank variables, or quantitative but not normally distributed for unrelated groups, were determined by the Kruskal-Wallis test or median test for 3 groups, and then pairwise or non-parametric Mann-Whitney test for each of the 3 pairs (groups 1 and 2, groups 1 and 3, groups 2 and 3), and for related groups (dynamic observations) by the Kendall test for 3 groups and then by the Wilcoxon test (Wilcoxon) for each of the 3 pairs (baseline, after 5 days and after 10 days).

Correlation was performed for quantitative variables according to Pearson and for rank variables according to Spearman. Statistical processing of the results was carried out using the Statistica program version 10.

**Results and discussion.** The nutritional status of patients in all three groups before surgery and during the 10-12 days of the postoperative period according to the methods of assessing nutritional status NRS, SGA and NRI was assessed as normal, moderate and severe malnutrition

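### Total bilirubin: the pooled 5-6 fold fall has no stated baseline and does not fit the arm averages from before surgery, and within-arm p-values stand in for a comparison of feeding routes

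*Combined protocol and SAP*

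**What the plan says.** Objective 2, in the protocol and again in the Report (Research objectives), covers protein and carbohydrate metabolism and "the consistency of liver function in cancer patients operated on for malignant tumors" under enteral, parenteral and mixed support.

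The Report's results text, which follows Methods of statistical data analysis, gives two accounts of total bilirubin.

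- **All groups together.** It refers to "high values of total blood bilirubin that persisted on the first day after surgery", puts the excess at more than tenfold above normal, and attributes it to temporary swelling of the biliary tract. For days 5-7 it then reports "a tendency towards a 5-6 fold decrease in its level from the initial values, which gradually decreased to normal values", the normal values being reached by days 10-12, although some patients stayed high until discharge.
- **By arm.** Enteral: "a decrease in the level of total bilirubin was recorded, on average, by 12.7% only by the 10th day after surgery" (p = 0.187). Parenteral: "on average, by 40.09% and by the 10th day by 45.0% from its initial values (preoperative period" (p = 0.002). Mixed: "a decrease, on average, by 20.0% by the 5th day and by 44.0% by the 10th day", with no p-value, described as slower.

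On testing, Methods of statistical data analysis says that differences between unrelated groups in rank or non-normal variables "were determined by the Kruskal-Wallis test or median test for 3 groups, and then pairwise" for each of the three pairs. Normally distributed variables go to Student's t test.

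**The concern.** The two accounts sit next to each other, and a reader will take them as describing the same patients. On the first, bilirubin largely normalised whatever the route. On the second, the enteral average hardly moved by day 10 and the other two arms fell by less than half. These give different answers on liver function, and the word that would reconcile them, 'initial', is not defined in the pooled statement.

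The second issue is the form of the evidence. One arm has a non-significant change, another a significant one, and the third has no p-value. It is easy to read this as showing that parenteral feeding clears bilirubin and enteral feeding does not. No test in the readable text supports that, although the methods name suitable between-group tests.

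**Working it through.** **Inputs.** The pooled fold change, the arm falls and the p-values come from the Report's results text. The arm sizes (31, 30, 30) come from its Research objectives section.

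**1. Pooled statement as a percentage.** Fall = 1 − 1/fold. Five-fold: 1 − 1/5 = 80.0%. Six-fold: 1 − 1/6 = 83.3%.

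**2. Arm falls as folds.** Fold = 1/(1 − fall).

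| Arm (n) | Day-5 fall | Fold | Day-10 fall | Fold | Printed p |
|---|---|---|---|---|---|
| Enteral (31) | not printed | – | 12.7% | 1/0.873 = 1.15 | 0.187 |
| Parenteral (30) | 40.09% | 1/0.5991 = 1.67 | 45.0% | 1/0.55 = 1.82 | 0.002 |
| Mixed (30) | 20.0% | 1/0.80 = 1.25 | 44.0% | 1/0.56 = 1.79 | none |

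**3. Can the arms combine to 5-6 fold?** Weighting by arm size:

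- Day 10: (31×12.7 + 30×45.0 + 30×44.0)/91 = 33.7%, or 1.51-fold.
- Day 5, enteral assumed unchanged: (0 + 30×40.09 + 30×20.0)/91 = 19.8%, or 1.25-fold.
- Day 5, enteral assumed already down 12.7%: 24.1%, or 1.32-fold.

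Other weights do not help. A weighted average cannot exceed the largest arm fall, which by day 10 is 45.0%. So from a preoperative baseline, with one kind of average, the 5-6 fold figure is not reproduced. The preoperative label is printed for the parenteral arm only; I assume it for the other two.

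**4. What a day-1 baseline would need.** If the pooled fall runs from day 1 and the arm falls run from before surgery, then day-1 level / preoperative level = fold × (1 − day-5 fall), taking days 5-7 as day 5.

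- Parenteral: 5×0.5991 = 3.00 to 6×0.5991 = 3.59.
- Mixed: 5×0.80 = 4.0 to 6×0.80 = 4.8.
- Enteral: 5×0.873 = 4.37 to 6×1 = 6.0, for an assumed day-5 fall between 12.7% and zero.

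Bilirubin would have had to rise roughly three- to six-fold from before surgery to day 1. A temporary excess of more than ten times normal is compatible with that. It is also coherent with the later course: from 10 times normal, a 5-6 fold fall leaves 10/5 = 2.0 to 10/6 = 1.67 times normal on days 5-7. But the text gives no preoperative level and no rise, and it says that the high values persisted, which suggests they were already there. The Report uses 'initial' in both senses: for basal metabolism it writes "from the initial value - 1-2 days of the postoperative period", and for parenteral bilirubin it means before surgery.

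**5. Other ways both could be true.**

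- *Jaundiced patients only.* If arm falls are means of patient percentages and all other patients were unchanged, the share falling 5-6 fold by day 5 would be 40.09/83.3 to 40.09/80.0 = 48-50% of the parenteral arm and 20.0/83.3 to 20.0/80.0 = 24-25% of the mixed arm. The readable text gives no such counts.
- *Different averages.* Suppose 15 patients fall from 20 to 3 times normal (85%) and 15 rise from 0.5 to 0.525 (5%). The mean patient fall is (85 − 5)/2 = 40%, while the mean level goes from 10.25 to 1.7625, a 5.8-fold fall.

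**6. Between-arm evidence.** Each arm's p-value compares that arm with itself. A route comparison needs the difference between arms and its own standard error, and neither is printed. The p-values attached to the pooled account (0.000 and 0.004) name no arm or contrast. The one comparative remark, that the mixed arm was slower, holds against parenteral at day 5 (20.0% against 40.09%). By day 10 the two are nearly equal (44.0% against 45.0%), and both exceed enteral (12.7%).

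**The case against.** The best defence is that the passage is loosely worded rather than wrong. The sentence just before the 5-6 fold statement describes a temporary day-1 peak, so a day-1 starting point is a natural reading. The by-arm text then labels a different, preoperative baseline for the parenteral arm. The pooled statement is also hedged as a tendency. This stands: a reader might infer that the Report contradicts itself, and the documents do not support that. They support only that the two accounts are not reconciled.

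A reader might also infer that the routes were never compared. That is too strong. The arms are set side by side, the methods name three-group and pairwise tests, and a figure placed after this text is not shown and may hold levels by arm. What can be said is that the readable text contains no formal comparison.

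It is tempting to work back from p = 0.187 and p = 0.002 to standard errors and so to an enteral-versus-parenteral test. The documents do not allow it. The methods send non-normal repeated measurements to the Kendall and Wilcoxon tests, and a rank-test p-value does not give the standard error of a mean. The parenteral p-value also follows both the day-5 and the day-10 figures without saying which it tests.

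Finally, a reader might think that the Report's conclusions fall with this. They do not. They concern nutritional scales, total protein and basal metabolism, and the Report credits drainage and tumour removal for the bilirubin fall.

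**Conclusion.** The point holds as a minor one, in two parts.

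First, a pooled fall of 80-83% by days 5-7 cannot describe the same average as arm falls of at most 40.09% at day 5 and 45.0% at day 10 if both start before surgery. This assumes one kind of average, the same patients, a preoperative baseline in all three arms, and an enteral day-5 fall no larger than the parenteral one. A day-1 baseline is a plausible explanation, but it is not stated and the text partly speaks against it. Only the source data can settle which explanation is right.

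Second, the liver-function part of objective 2 is not answered for bilirubin by within-arm p-values in two arms and none in the third. The documents support neither a difference between routes nor its absence.

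**What to change.** 1. State the baseline, the population and the kind of average behind the 5-6 fold and normal-by-days-10-12 statements. If they apply only from day 1, or only to patients jaundiced before surgery, say so and give the number per arm. Correct them if they are meant from the preoperative value and do not hold.
2. In place of the within-arm p-values, compare day-10 total bilirubin between arms, adjusted for preoperative bilirubin. The log scale suits skewed values. Report one three-arm test, then the three pairwise ratios with 95% confidence intervals.

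The cost is a small re-analysis of one laboratory variable already collected and a few corrected sentences; no new patients or measurements are needed. The drawback is precision: at about 30 per arm the intervals will be wide, and the honest answer may be that the routes cannot be separated on bilirubin.
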